3.2 SECONDARY OUTCOME(S)

Secondary study endpoints, events, or outcomes you will be evaluating or observing.

Secondary outcomes include:

- Fall rates
- Quality of life

3.3: EXPLORATORY OUTCOME(S)

Other exploratory variables include:

- Functional strength and balance
- Social resources
- Readiness
- Self-regulation
- Pain (intensity and impact on function)
- Medication inventory
- Sex as a biological variable
- Covid 19 (impact of mitigation/ containment efforts on health and physical activity)

CHAPTER 4 - STUDY INTERVENTION

4.1: DESCRIPTION

Intervention description.

Dose and delivery. We carefully considered the dose of 8 weekly contacts, each lasting 90 minutes, based on triangulated data from our prior research and feedback from community stakeholders. Our prior research⁹ and the CDC compendium of fall prevention interventions⁶¹ describe a broad range of doses that elicit promising effects with 8 weeks-12 contact hours on the low side of the range and 52 weeks-104 contact hours on the high side of the range. Also, our preliminary studies showed intervention session attendance was good across conditions and in post-intervention interviews, participants indicated this dose was acceptable: some even suggested we increase intervention duration to 12 weeks. Community stakeholders including older adults, center leaders, and healthcare providers advised us to increase the amount of time spent during contacts from 60 minutes to 90 minutes to ensure participants did not feel “rushed.” They also advised us to conduct intervention and data collection meetings between 9 am and 4 pm, and to limit group size to 4-6.

Adjustments for Coronavirus: March 17, 2020

Intervention visits in this study are done in small group (4 to 6 people) gatherings during which we practice the Otago Exercise Program movements together, and a coach facilitates discussions focused on behavior change strategies being tested. We enroll one cohort of 16 to 24 participants at a time, so they can complete the 8-week course. In

light of the current situation, we will delay future cohorts until we are able to deliver the small group intervention in person again.

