However, our current cohort (11 of 13) is in week 6 of the 8-week intervention. Thus, we plan to conduct these by phone conferencing using UMN Zoom. We will not use the video portion of Zoom because not all participants have access to the internet. We will conduct each meeting according to our intervention manual, which delineates topics for discussion and exercise per Otago protocol. Similar to in-person intervention meetings and when participants perform these exercises at home independently (2 times per week to every day), there is a small risk of discomfort or injury. Consistent with our protocol and the Otago Exercise Program manual we will minimize the risk using several strategies. First, the exercises in Otago are considered safe for older adults, including those with frailty and multiple chronic conditions. Second, we will ensure that all phone conference participants have water, and are near sturdy structures during the exercises, such as a non-rolling chair or a counter. Third, we will remind participants to stop exercising if they feel discomforts such as joint pain or shortness of breath. Finally, at this point in the intervention, all participants who will participate in the conference call have mastered the exercises and know how to personally adapt them according to ability, comfort, and preferences.

Table 3 highlights condition and content by time. Each contact is 90 minutes: 10 for questions and answers; 40 for Otago PA; 20 for interpersonal behavior change strategies; 20 for intrapersonal behavioral change strategies; and, in lieu of behavioral change strategies--20-40 for attention control topics related to Health & Age, based on the National Institute of Aging website, Health & Aging.⁶²

Table 3. Condition, Content, and Time

Time in Minutes	Condition and Content			
	Otago/PA	Otago/ PA + Inter-personal	Otago/ PA + Intra-personal	Otago/ PA + Inter-personal + Intra-personal
10	Q& A	Q&A	Q&A	Q&A
40	Otago	Otago	Otago	Otago
20	Health & Age	Inter-personal	Health & Age	Inter-personal
20	Health & Age	Health &Age	Intra-personal	Intra-personal

The social milieu in each small group meeting will support friendly and positive interactions and discussions guided by curricula topics and objectives. All content (experimental, attention control, core) is summarized in the next six paragraphs.

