5.1 STUDY DESIGN

Experimental. We will address this proposal's aims and hypotheses using a 2x2 factorial experiment where one factor represents receipt of an interpersonal intervention component (No vs Yes) and the second factor represents receipt of an intrapersonal intervention component (No vs Yes). Three hundred and eight community-dwelling older adults will be randomized to 1 of 4 conditions, which represent distinct combinations of experimental components (sets of interpersonal and intrapersonal behavior change strategies) and core intervention content (evidence based physical activity protocol and a physical activity monitor). The study will be implemented in 13 waves over 48 months, within Minneapolis and St. Paul community centers. Interventions for each condition will be delivered to small groups of participants (4-6) randomized to the same condition. These small groups will meet every week for approximately 90 minutes over the course of 8 weeks.

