 - Pain via the Brief Pain Inventory-short form (Tan, 2004; Mendoza, 2006)^{89,90}
 - Medication Inventory (see Appendix 2)
 - Self-reported health and Fall Risk (Stevens, 2013; Kunkel, 2011)^{55,75}
 - Impact of the COVID-19 Pandemic and Accompanying Mitigation Efforts on Older Adults' physical activity and wellbeing¹¹⁰
 - Social Support and Exercise Survey (Family and Friends) (Sallis et.al , 1987)⁸⁰
 - Duke--UNC Functional Social Support Questionnaire*
 - Index of Readiness (Fleury, 1994)²²
 - Self-Efficacy for Exercise (Resnick & Jenkins, 2000)⁸¹
 - Index of Self-Regulation (Fleury, 1998)⁸⁴
 - Physical Activity Enjoyment Scale-8
 - Behavioral Regulation in Exercise Questionnaire (Markland & Tobin, 2004)⁸³
 - Life-Space Mobility¹¹¹
 - Physical Function-Short Form-6b (PROMIS; Rose, 2008)⁷⁹
 - Physical Activity Scale For The Elderly PASE⁷²
 - Health and Physical Activity Resources Survey (CIRS)¹¹²
 - Group Cohesion**
 - Quality of Life: Global Health Scale Patient-Reported Outcomes Measurement Information System, including items that address physical and social function (PROMIS) (Hays, 2009)⁷⁶

*Administered at baseline only

**Administered immediately post-intervention only

Coronavirus adjustments: March 17, 2020

Assessment visits, which are structured interviews lasting approximately 45 to 90 minutes, will occur over the phone for the duration of new Coronavirus recommendations. We will notify the participants of this change. Our researchers will adjust their schedules according to our participants' availability and mail them information as needed.

The SPPB portion of the assessments, which require in person observation, will be delayed until Coronavirus restrictions are lifted.

Observations of functional strength and balance include the Short Physical Performance Battery at baseline; immediately post-intervention; 6 months' post-intervention; and 12 months post-intervention.⁷⁷ This battery includes timed repeated chair stand, semi-tandem, side by side, tandem balance testing, and a timed walk. Scores for each item are summed for a total score

ranging from 0-12 (12 indicates no impairments). The gradient of resulting scores validly reflects variation in lower extremity strength in older adult populations, and is predictive of progressive disability. It also demonstrates that the timed walk is predictive of catastrophic disability. The test will be discontinued if either the participant or the RA perceives it is unsafe to proceed.

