7.1 DISSEMINATION

We will share protocol content and study findings with interested participants, community partners, and public health officials in Minnesota. Our dissemination plan has three main facets. First, we will publicly present information about all aspects of this proposal; study protocol; intervention content; recruitment and retention strategies; and findings local meetings within community centers. We will also make annual presentations locally through the UMN School of Nursing's Annual Research Conference; during meetings with community partners; and during Minnesota's annual Fall Awareness Day.¹⁰¹ Second, we will develop a website for the study where we will post information about PA and falls and post summaries of our presentations on this Web site, written in plain language for a general audience. Third, we will provide participants with a report of their personal results pertaining to their balance, leg strength and PA.

CHAPTER 8 – STUDY DURATION

- The duration anticipated for an individual participant's participation in the study: **15 to 18 months**
- The duration anticipated to enroll all study participants: **4 years**
- The duration anticipated to complete all study procedures and data analysis: **6 years (given COVID-19)**

CHAPTER 9 – STUDY POPULATION

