week). The factors, or independent variables, are interpersonal and intrapersonal components; each with two levels indicating exposure (No vs Yes). Different models will be developed for PA measured objectively. PA will also be measured via self-report. Each model will include baseline PA values as a covariate. Main and interaction effects of the components on the duration of PA will be tested immediately, 6 months, and 12 months post- intervention. Further, we will apply multilevel longitudinal data analyses to examine the variation of component effects across time-points (baseline; immediately post-intervention; 6 months' post-intervention; and 12 months' post- intervention), including interactions between components (e.g. interpersonal x intrapersonal x time), which will allow us to see when an older adult might benefit from additional support to maintain PA.

Secondary Aim: The secondary outcome of Falls will first be described using the number of falls, fallers, fall rate, and time to first fall post-intervention.⁷⁴ Given the expected distribution of falls, we will use negative binomial regression models to estimate the between-group difference in fall rates 12 months' post-intervention. Quality of Life data will be assessed using 2x2 full factorial ANCOVA and longitudinal analyses described for Aim 1 with total mean QOL as the outcome variable.

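### The primary and secondary models name no wave or calendar-period term, although on even wave spacing about 46% of 12-month assessments fall after 17 March 2020; the cost is mainly precision

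*Combined protocol and SAP*

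**What the plan says.** Section 5.1: "The study will be implemented in 13 waves over 48 months". Chapter 8 gives four years for enrolment. Section 4.1 adds "We enroll one cohort of 16 to 24 participants at a time", delivered in small groups of 4 to 6 by condition.

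Under the March 2020 adjustment in section 4.1, "our current cohort (11 of 13) is in week 6 of the 8-week intervention". That cohort's remaining sessions move to telephone conferencing. For later cohorts the plan is that "we will delay future cohorts until we are able to deliver the small group intervention in person again". Section 5.2 says assessment visits, described as structured interviews, "will occur over the phone for the duration of new Coronavirus recommendations". It states no change to Fitbit capture.

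For the primary 2x2 ANCOVA, section 17.1 says "Each model will include baseline PA values as a covariate" and names no other covariate. Quality of life follows the same approach, and falls use negative binomial regression with no covariate named. The longitudinal models have component-by-time terms, where time is the study visit. A general clause adjusts for confounders that emerge from comparing the conditions. COVID-19 enters the analysis plan as an exploratory, stratified effect modifier beside pain, medication and sex, without a definition of its strata. Section 17.4 says dates will be shifted when the study is complete.

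**The concern.** Each wave has its own calendar period and season, and a cohort of 16 to 24 is the size of four groups of 4 to 6. Wave is therefore a natural block. A change in PA that affects a whole wave is noise in a comparison of conditions unless the model removes it. The confounder clause does not help, because a period effect spread evenly over the conditions would never show up as a difference between them.

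Interpretation is also at stake. The primary hypothesis concerns the interpersonal component, which works through social routines, support and community resources. Section 17.1 intends to use component-by-time terms to see when participants need more support to maintain PA. If later visits fall more often after March 2020, a component weakened by the pandemic would look like one that fades.

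**Working it through.** **1. The plan's own figure.** The documents give no share of assessments by period. The nearest figure is 80% power with N = 308 for an effect of 0.20 (section 17.2). After 15% attrition, 308 x 0.85 = 262, or 131 per factor level. Then 0.20/√(2/131) = 1.62, and power is Φ(1.62 − 1.96) = 0.37. Reaching 0.80 needs √(1 − ρ²) = 1.62/2.80 = 0.578, so a baseline-to-outcome correlation ρ of about 0.82 (about 0.78 if all 308 count). The plan states no such correlation. That is a separate matter; ρ near 0.8 is used here only to scale the residual variance.

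**2. Calendar.** I read the cohort count as wave 11 of 13; as a headcount, 13 would be below the stated minimum of 16. Week 6 of 8 puts the start about 5.5 weeks before 17 March 2020. The 12-month visit comes 8 weeks plus 12 months after the start. An earlier wave therefore has its 12-month visit after the date if it started no more than 12 months + 2.5 weeks = 12.6 months before wave 11. For the 6-month visit the limit is 6.6 months.

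At 48/13 = 3.69 months' spacing, 12.6/3.69 = 3.4, which adds waves 8 to 10. For the 6-month visit, 6.6/3.69 = 1.8, which adds wave 10. Waves 11 to 13 count at every post-intervention visit.

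| Wave spacing (months) | Immediate | 6 months | 12 months |
|---|---|---|---|
| 1.84 (8-week courses back to back) | 3/13 | 6/13 | 9/13 (69%) |
| (48 − 14)/12 = 2.83 (48 months includes follow-up) | 3/13 | 5/13 | 7/13 (54%) |
| 48/13 = 3.69 or 48/12 = 4 | 3/13 (23%) | 4/13 (31%) | 6/13 (46%) |
| 4.5 to 6 | 3/13 | 4/13 | 5/13 (38%) |

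Shares of waves equal shares of assessments only if waves are of similar size.

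**3. Variance.** A shift of δ SD in a share p of assessments adds δ²p(1 − p) to a unit variance. With δ = 0.3 and p = 0.2, this is 0.09 x 0.16 = 0.014. With δ = 0.5 and p = 0.5, it is 0.25 x 0.25 = 0.0625. Both δ and this range of p are assumptions. At ρ = 0.8 the residual variance is 1 − 0.64 = 0.36, so the addition is 0.0144/0.36 = 4% to 0.0625/0.36 = 17% of it. The standard error rises by √1.04 to √1.17, or 2% to 8%. With no baseline correlation the rise would be 0.7% to 3.1%.

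**4. Power.** A simulation used 3,000 runs, 260 evaluable participants, conditions balanced within wave, ρ = 0.815, a true effect of 0.20, and the shift applied to outcomes in waves 8 to 13.

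| Shift | Power without period term | Power with period term |
|---|---|---|
| 0.3 SD | 0.78 | 0.78 |
| 0.5 SD | 0.74 | 0.79 |
| 0.8 SD | 0.64 | 0.80 |

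The mean estimate was about 0.20 throughout. With no true effect, the model without the term rejected in 2.9% of runs at 0.5 SD and 2.0% at 0.8 SD, so the omission is conservative.

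**5. Time and period.** On even spacing the share after March 2020 rises from 3/13 to 4/13 to 6/13 across visits. Suppose, for illustration only, that a component's effect is 0.20 before the date and zero after it. The averages would be 0.20 x 10/13 = 0.15, 0.20 x 9/13 = 0.14 and 0.20 x 7/13 = 0.11. This looks like decay although nothing faded with time since the intervention.

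**6. Component by period.** The standard error relative to a main effect is 1/√(p(1 − p)). At p = 6/13 this is 1/√0.2485 = 2.0. If the main effect has 80% power at 0.20, the difference between periods needs about 0.40 and has about 29% power at 0.20.

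**The case against.** The effect on the main result is modest and rests on assumed shifts. At 0.3 SD the simulation shows no visible loss. Omitting a balanced block makes the test conservative, and clustering within small groups, a separate matter, works in the opposite direction. In cohorts 12 and 13 the baseline was probably also measured after March 2020, so the baseline covariate may absorb part of the shift; the simulation ignored this. All of this stands and limits the size of the point.

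Four stronger readings are tempting, and the documents do not support them.

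- A reader might infer that delivery in general moved to the telephone. Only the last sessions of cohort 11 did; later cohorts were to wait for in-person meetings.
- A reader might infer that no split by COVID-19 is planned. Section 17.1 plans one as exploratory, and the power in step 6 makes that label reasonable. What is missing is a date definition.
- A reader might infer that the telephone change affects the primary outcome as a whole. It concerns interviews, so of the two PA measures only self-report changes mode. Accelerometer PA is exposed to the period, not the mode.
- A reader might infer that the main effects are biased. Individual randomisation and the cohort size point to rough balance by wave, although section 5.2 lets delayed starters join a later course.

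It is also true that a visit after 17 March 2020 is not necessarily a visit under restrictions; no end date is given.

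**Conclusion.** The gap is real and worth closing as a matter of precision and interpretation. Under even spacing, 46% of 12-month and 31% of 6-month assessments fall after 17 March 2020. The 12-month figure runs from about 38% to 69% under other spacings and is an inference, since no wave dates are given. For an assumed shift of 0.3 to 0.5 SD, the unmodelled period variance is about 1% to 6% of the total and, at ρ near 0.8, about 4% to 17% of the ANCOVA residual variance. Balance of conditions within wave is inferred from cohort size, as no blocking is described. A wave term would also protect against chance imbalance by wave. Because wave is constant within a participant, it cannot by itself separate period from visit time in the longitudinal models.

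**What to change.** In section 17.1:

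- Add wave, as randomised, as a fixed effect in the ANCOVA models (PA and quality of life) and in the negative binomial model for falls.
- In the longitudinal models, also add a visit-level indicator for before or after 17 March 2020.
- Define by date the COVID-19 stratum already planned as exploratory. Report the component-by-period estimate with its confidence interval, labelled as low-powered, and read the component-by-time results beside it.
- In the models for self-reported PA, but not accelerometer PA, add an indicator for telephone or in-person assessment.
- Derive and keep the wave and period variables before dates are shifted at study completion (section 17.4).

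The cost is SAP wording, minor analysis work and 12 degrees of freedom out of about 262 (13 where the period indicator is added). No change to data collection is proposed.

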5.4 FOLLOW-UP

Please Refer to section 5.3 above

CHAPTER 6 – DATA BANKING

Not Applicable

CHAPTER 7 – SHARING OF RESULTS WITH PARTICIPANTS

7.1 DISSEMINATION

We will share protocol content and study findings with interested participants, community partners, and public health officials in Minnesota. Our dissemination plan has three main facets. First, we will publicly present information about all aspects of this proposal; study protocol; intervention content; recruitment and retention strategies; and findings local meetings within community centers. We will also make annual presentations locally through the UMN School of Nursing's Annual Research Conference; during meetings with community partners; and during Minnesota's annual Fall Awareness Day.¹⁰¹ Second, we will develop a website for the study where we will post information about PA and falls and post summaries of our presentations on this Web site, written in plain language for a general audience. Third, we will provide participants with a report of their personal results pertaining to their balance, leg strength and PA.

CHAPTER 8 – STUDY DURATION

- The duration anticipated for an individual participant's participation in the study: **15 to 18 months**
- The duration anticipated to enroll all study participants: **4 years**
- The duration anticipated to complete all study procedures and data analysis: **6 years (given COVID-19)**

CHAPTER 9 – STUDY POPULATION

9.1 INCLUSION CRITERIA

All potential participants will be screened by trained study staff for inclusion based on the following criteria:

Inclusion Criteria:

- ≥70 years of age
- English speaking
- Low PA as determined by the Rapid Assessment of Physical Activity Survey⁵⁴
 - Aerobic sub score 1-4 – Does not participate in endurance exercise such as walking more than 150 minutes per week, and / or
 - Strengthening/Balance activities sub score of 0 – Does not participate in strengthening and/or balance exercises more than once per week
- One or more fall risk factors as determined by CDC, Steadi fall risk screener⁵⁵
 - One or more falls in the last year
 - Unsteadiness when standing or walking
 - Worries about falling
- Participants who self-report the following symptoms will require clearance from a primary provider (as guided by the Exercise and Screening for You Questionnaire):⁵⁶
 - Pain, tightness or pressure in chest during PA (walking, climbing stairs, household chores, similar activities) *that have not been checked and/ or treated by a healthcare provider*
 - Current dizziness *that have not been checked and/ or treated by a healthcare provider*
 - Current, frequent falls *that have not been checked and/ or treated by a healthcare provider*

9.2 EXCLUSION CRITERIA

Exclusion criteria for participation in this study include:

- Lower extremity surgery within the past 6 weeks
- Inability to walk
- Formal diagnosis of neurocognitive impairment or Callahan Dementia Screener score of < 5.

9.3 SCREENING

Screening: A trained study staff will screen potential participants via telephone interviews using the screening case report form in Research Electronic Data Capture (REDCap), which includes questions about:

- Age

- History of lower extremity surgery Fall risk factors
- Three short surveys:
 1. The Exercise and Screening for You (EASY)⁵⁶
 2. The Rapid Assessment of Physical Activity⁵⁴
 3. The Callahan Screener for Cognitive Dysfunction¹¹³
 - Repeat the following words (apple, table car)
 - What is the year
 - What is the month
 - What is the day
 - Remember the words we just talked about (apple, table, car)

CHAPTER 10 – VULNERABLE POPULATIONS

This study does not include vulnerable populations; however, we will not exclude older adults with variable levels of functional capacity or the economically disadvantaged. Approximately 36% of older Americans report having difficulty performing one or more activities of daily living; and 9.5% report incomes below the poverty level.¹⁰⁸ Thus, these populations should not be excluded from intervention studies designed to increase PA, reduce falls, and improve QOL.

CHAPTER 11 – NUMBER OF PARTICIPANTS

11.1: NUMBER OF PARTICIPANTS TO BE CONSENTED

308

CHAPTER 12 – RECRUITMENT METHODS

